**Multicenter double-blind placebo-controlled parallel group
randomized clinical study of efficacy and safety of Raphamin in the
treatment of acute respiratory viral infection in children aged 12-18
years**

Phase III

Sponsor	ООО «NPF «MATERIA MEDICA HOLDING»
Protocol number	MMH-407-003
Version date:	November 10, 2020
ClinicalTrials.gov Id:	NCT04918771

Protocol Summary

This document represents the protocol summary for the study on human patients. The study will be carried out in accordance with ICH GCP, Helsinki Declaration of World Medical Association, Rules of good clinical practice, approved by order of the Ministry of Health of the Russian Federation dated April 1, 2016 N 200n, , relevant requirements of the regulatory authorities as well as the study procedures.

Title of Study

Multicenter double-blind placebo-controlled parallel group randomized clinical study of efficacy and safety of Raphamin in the treatment of acute respiratory viral infection in children aged 12-18 years.

Phase: III

Sponsor: OOO «NPF "MATERIA MEDICA HOLDING», Moscow, Russia

Protocol No. MMH-407-003

Objective of the study

- To evaluate the efficacy and safety of Raphamin in the treatment of acute respiratory viral infection (ARVI) in children aged 12-18 years.

Endpoints

Primary endpoint

1. Time to resolution of ARVI^{1,2} symptoms (PCR-confirmed).

Secondary endpoints

1. ARVI severity (clinically diagnosed and/or PCR-confirmed; based on the area under the curve (AUC) results for the total severity index³ from days 1 to 6 of observation).
2. Percentage of patients with resolution of ARVI symptoms (clinically diagnosed and/or PCR-confirmed).
3. Time until resolution of ARVI symptoms, (clinically diagnosed and/or PCR-confirmed).
4. Percentage of patients with resolution of ARVI symptoms (PCR-confirmed).

¹Time from symptom onset at visit 1 until resolution of the disease symptoms.

Resolution of ARVI symptoms will be defined if temperature is $\leq 37.3^{\circ}\text{C}$ within 24 hours (without further increase during observation period) + lack/presence of systemic ARVI symptoms ≤ 2 .

² Based on a patient diary.

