The nasopharyngeal swabs for PCR diagnosis and verification of respiratory viruses will be performed prior to therapy to confirm the viral etiology of ARVI. To exclude the infection caused by the new coronavirus COVID-19 (Coronavirus disease 2019), a rapid test for SARS-CoV-2 antigen will be made. In case of a positive SARS-CoV-2 test, the physician will act in accordance with the current version of the Ministry of Health of the Russian Federation Temporary methodological recommendations "Prevention, diagnosis, and therapy of new coronavirus infection (COVID-19)".

If a patient meets all inclusion criteria and does not have any exclusion criteria, at Visit 1 (Day 1), he/she will be randomized into one of two groups: patients of group 1 will take Raphamin according to the dosage regimen for 5 days; patients of group 2 will take Placebo using Raphamin 5-day regimen.

The study will use an electronic patient diary (EPD) for recording morning and evening axillary

⁴ Based on a patient diary.

body temperature (using a classic mercury-free thermometer) and disease symptoms (Symptom Severity Score). Besides, antipyretic dosing (if applicable) and any worsening in a patient's condition (if applicable, for safety evaluation/AE registration) will also be recorded in a patient diary. The investigator will provide instructions on filling the diary. At Visit 1 the parent/adoptive parent together with an investigator will record ARVI symptom severity and body temperature in the diary.

Patients will be observed for 14 days (screening, randomization - up to 1 day, treatment period – 5 days, follow-up – up to 2 days; deferred "phone visit" – day 14).

During the treatment and follow-up period the patients/physicians will pay 3 visits and the fourth "phone visit" will be scheduled additionally: 1) visits by physician/patient - on Days 1, 5, and 7 (Visits 1, 2, and 3) - in a study center or at home; 2) "phone visit" (Visit 4) - on Day 14.

At Visits 2 and 3, the investigator will perform an physical examination, document changes in the symptoms and concomitant medications, and check patient diaries. At Visit 3 laboratory tests will be performed and compliance will be checked.

"Phone visit" will be performed to interview parents/adoptive parents about the patient's condition, presence/absence of secondary bacterial/viral complications, and use of antibiotics.

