14. Medical history of mental diseases of the patient or their parent(s)/adoptive parents.
15. Participation in other clinical trials for 3 months prior to enrollment in this study.
16. Patient's parents/adopters who are related to any of the on-site research personnel directly involved in the study or are an immediate relative of the investigator. 'Immediate relative' means husband, wife, parent, son, daughter, brother, or sister (regardless of whether they are natural or adopted).
17. The patient's parent/adopter who works for OOO "NPF "MATERIA MEDICA HOLDING" (i.e. the company's employees, temporary contract workers, designated officials responsible for carrying out the research or any immediate relatives of the aforementioned).

Criteria for Withdrawal or Termination

1. Screening failure.

2. Failure or refusal of the patient to follow the protocol.
3. The necessity to use medications not permitted in the study.
4. An adverse event requiring discontinuation of the study drug.
5. Patient's or his/her parent's/adopter's decision to withdraw early for lack of efficacy or other reasons.
6. Pregnancy.
7. Cases not stipulated in the protocol where the investigator decides that further participation may harm the patient.
8. Eligibility error.

Number of patients

It is planned to include 400 patients, 360 of them will be randomized which is expected to yield at least 200 patients (100 per Raphamin and Placebo groups) completing all the protocol procedures.

Interim analysis

The protocol does not schedule unblinded interim analyses. At the sponsor's decision, blinded interim analysis may be carried out to specify population parameters and potential further specification of sample size (increase only).

Treatment

Group I

Name of the medicinal product: Raphamin

Active ingredient: affinity purified antibodies to human interferon-gamma – 10 000 UMA*,
affinity purified antibodies to CD4 – 10 000 UMA,
affinity purified antibodies to β 2-microglobulin major histocompatibility complex class I – 10 000 UMA,
affinity purified antibodies to β 1-domain of major histocompatibility complex class II – 10 000 UMA

* UMA – Units of Modifying Activity.

Excipients: lactose monohydrate, microcrystalline cellulose, magnesium stearate.

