Method of administration: Per os without food. The tablet should be held in mouth until completely dissolved. On the first day of treatment, take 8 tablets according to the following scheme: 1 tablet every 30 minutes for the first 2 hours (total 5 tablets in 2 hours), then during the same day take another 1 tablet 3 times at equal intervals. On the 2nd day and beyond, take 1 tablet 3 times a day. The duration of treatment is 5 days.

Dosage form: Tablet for oral use.

Description: Flat, cylinder-shaped, scored beveled edge, white to off-white tablets.

Storage conditions: At temperature below 25°C. Keep out of the reach of children.

Group 2

Name of the medicinal product: Placebo

Active ingredient: N/A

Excipients: lactose monohydrate, microcrystalline cellulose, magnesium stearate.

Method of administration: Per os without food. The tablet should be held in mouth until completely dissolved. On the first day of treatment, take 8 tablets according to the following scheme: 1 tablet every 30 minutes for the first 2 hours (total 5 tablets in 2 hours), then during the same day take another 1 tablet 3 times at equal intervals. On the 2nd day and beyond, take 1 tablet 3 times a day. The duration of treatment is 5 days.

Dosage form: Tablet for oral use.

Description: Flat, cylinder-shaped, scored beveled edge, white to off-white tablets.

Storage conditions: At temperature below 25°C. Keep out of the reach of children.

Treatment duration

Raphamin/Placebo treatment duration is 5 days.

Observation period

Overall, the patient will be observed for 14 days (screening, randomization for 1 day, treatment for 5 days, follow-up for 2 days; late-scheduled phone visit on day 14).

Symptomatic (Standard) treatment

Throughout the study the patients may receive medications for symptomatic treatment of ARVI:

- antipyretic/non-steroidal anti-inflammatory drug (paracetamol/ibuprofen)
and/or
- nasal vasoconstrictive agent – oxymetazoline/naphazoline
and/or
- cough suppressant/expectorant – butamirate/ambroxol, bromhexine, guaifenesine, acetylcysteine.

Indications for antipyretics

Increased body temperature ($> 38.5^{\circ}\text{C}$) in subjects without complications and comorbidities and $> 38.0^{\circ}\text{C}$ in subjects with concomitant pulmonary, cardiac, nervous system diseases.

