Schedule of study procedures

Procedure/Visit	Visit 1 (Day 1)	Visit 2 (Day 5±1)	Visit 3 (Day 7±1)	Visit 4 (Day 14±1)
Informed consent	+			
Registration of a study patient in the IVRS* and assignment of patient ID	+			
Complaints collection	+	+	+	
Medical history	+			
Concomitant diseases and conditions	+	+	+	+
Physical examination	+	+	+	
ARVI symptoms	+	+	+	
Concomitant therapy	+	+	+	+
SARS-CoV-2 rapid test	+			
Pregnancy test	+			
Inclusion/exclusion criteria	+			
Randomization	+			
Nasopharyngeal swabs for PCR	+			
Safety laboratory tests**	+		+	

Procedure/Visit	Visit 1 (Day 1)	Visit 2 (Day 5±1)	Visit 3 (Day 7±1)	Visit 4 (Day 14±1)
Study drug supply	+			
Antipyretic drug supply	+			
Evaluation of the study drug safety	+	+	+	+
Patient diary	+	+	+	+
Study drug accountability and return			+	
Treatment compliance			+	
Visit completion	+	+	+	+
Telephone survey				+
Study completion***				+

* Interactive voice/web response randomization system
 ** Laboratory tests include hematology, urinalysis, serum chemistry (total protein, C-reactive protein, glucose, total bilirubin, creatinine, ALT, AST, cholesterol). Performed with availability of signed PIS and ICF including the patient's consent for blood and urine sampling.
 *** In case of early withdrawal the procedure may be carried out at Visits 1, 2 or 3.

Statistical Analyses

SAS-[9.4].⁵ will be used for data processing and statistical calculations.

Samples

Total set: all enrolled patients who have signed ICF. This sample will consider all the recorded AEs, including those occurred prior to the study therapy.

Safety population: all included and randomized patients who received at least one dose of the study drug. This sample will be used for **analysis of the study treatment safety and tolerability**, as all adverse events identified after the study drug administration will be recorded.

Full Analysis Set. This sample includes all enrolled patients, except for those who met at least one of the following events:

- 1) non-compliance with inclusion / exclusion criteria;
- 2) patient did not take a single dose of the study drug;
- 3) lack of any data about the patient after administration of the study drug.

This sample, the most consistent with the “Intention-to-treat” principle, will be used for the **Intention-to-treat analysis (ITT analysis)** of the study therapy efficacy.

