⁹ This rate is composite: 10% patients will be screening failures or discontinue the study for other reasons specified in the relevant protocol section, in 44.4% remaining patients the diagnosis will not be confirmed by PCR. The rate was assessed based on PCR findings obtained in "Multicenter double-blind placebo-controlled randomized parallel-group study of efficacy and safety of MMH-407 in the treatment of acute respiratory viral infection" (MMH-407-001).

various reasons, at least **400** patients will be required to sign informed consent, with **200** subjects per group.

Statistical criteria

All the statistical calculations will be performed using two groups of statistical criteria:

- parametric – to obtain effective evaluations for parameters of random values, if the relevant conditions of applicability of methods/models are not violated (e.g. sphericity, normality, proportionality of risks, etc.);
- non-parametric – in any other cases.

Parametric criteria

The application of parametric criteria will be accompanied by a check of models for applicability (e.g. Kolmogorov-Smirnov test, Shapiro-Wilk test, etc.).

The following parametric tests and approaches are to be used:

1. To evaluate the differences of continuous variables obtained in one group at two different visits – Student's test for matched samples.
2. To evaluate the temporal dynamics of the compared indicators – analysis of variance (ANOVA) or covariance (ANCOVA) in the modification with repeated measures.
3. In case of multiple comparisons between the groups will apply a variety of corrections for multiplicity (Dunnett, Tukey, Scheffe, Holm adaptive test), etc.
4. In case of abnormal data distribution, approaches with the Generalized Linear Models and / or Mixed Linear Models will be used.
5. Selection of the type of distribution, specification of the factor and covariance structures of the model will be made using fit-statistics such as AIC¹⁰ (Akaike information criterion).

To perform the above-mentioned statistical tests and techniques, it is assumed that the following SAS procedures are used:

- UNIVARIATE – check for normality of the compared distributions;
- CORR, MEANS – calculation of descriptive statistics;
- TTEST – Student t-test with all the modifications;
- GLM – analysis of General Linear Models for studying temporal dynamics (ANOVA, ANCOVA);
- GENMOD – analysis of Generalized Linear Models;
- MIXED – analysis of Mixed Linear Models.

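### No test is assigned to the time-to-resolution primary endpoint, non-normal data are sent two ways without a priority, and Full Analysis Set withdrawals have no time or censoring rule

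*Combined protocol and SAP*

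**What the plan says.** **Endpoint and hypothesis.** The primary endpoint is time to resolution of PCR-confirmed ARVI symptoms, taken from the diary. Resolution requires that temperature stays down "without further increase during observation period". Evaluation of sample size, item 1.6, states the hypothesis as M1 - M2, a difference in average times, and uses the two-means formula.

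**Choice of method.** Statistical criteria names two families. The first is "parametric – to obtain effective evaluations for parameters of random values, if the relevant conditions of applicability of methods/models are not violated", where the conditions listed include normality and proportionality of risks. The second, non-parametric methods, covers every remaining case. Parametric criteria adds checks such as Kolmogorov-Smirnov and Shapiro-Wilk. Its item 4 sends non-normal data to generalized or mixed linear models, and item 5 selects the distribution by fit statistics such as AIC. TTEST, GENMOD, NPAR1WAY, LIFETEST and PHREG are listed as available procedures, and none is linked to the primary endpoint. The only Student's test among the numbered items is the within-group, matched one.

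**Withdrawals.** Withdrawal criterion 5 foresees a "decision to withdraw early for lack of efficacy or other reasons". The Full Analysis Set drops patients for an eligibility breach, for no dose, or for "lack of any data about the patient after administration of the study drug". A patient who leaves after some diary entries therefore stays in. Footnote 6 settles Per Protocol eligibility when the recovery time can still be determined; it does not supply a value for anyone else.

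**Length of recording.** Observation period says "Overall, the patient will be observed for 14 days". The Schedule of study procedures marks "Patient diary" at Visit 4 (Day 14) but "ARVI symptoms" only to Visit 3 (Day 7).

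**The concern.** Three things are left open for the confirmatory comparison.

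- **The test.** Checks on the trial data choose it, and the plan gives non-normal data two destinations (generalized or mixed model, or non-parametric test) without ranking them.
- **The quantity tested.** A generalized model can keep a comparison of means. Mann-Whitney asks whether times in one arm tend to be shorter, which is not M1 - M2. The estimand can therefore change with the data.
- **The value for an unresolved withdrawal.** A comparison of means needs a time for every patient. The listed procedures that accept censored times are not tied to this endpoint.

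At stake are the meaning of the primary result, its power, and room to choose an analysis after the data are seen.

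**Working it through.** **1. The plan's own size.** Inputs from Evaluation of sample size: two-sided alpha 0.05, power 80%, SD 2.5 days, ratio 1:1. The difference is worded as below 1 day; 1.0 day is the value that reproduces the stated number.

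n per arm = (1.960 + 0.842)² × 2 × 2.5² / 1² = 98.1, rounded up to 99, or 198 in total against the stated 200. Power at 100 per arm is Φ(1/(2.5 × √(2/100)) - 1.960) = Φ(0.868) = 80.7%. Inflation: 200/(1 - 0.5) = 400. The composite rate in footnote 9 also holds: 400 × 0.9 = 360 and 360 × 0.556 = 200. The arithmetic is sound, and it is for a comparison of means.

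**2. What the candidate tests do at that size.** The documents give no distribution and no placebo mean, so these are assumed: lognormal, gamma or Weibull times on a half-day grid, placebo mean 4, 5 or 6 days, true difference 1.0 day, 100 per arm, all times observed. SD 2.5 is the plan's upper limit; SD 2.0 is an assumed lower value. Results at SD 2.5 (%; 4000 trials per cell, 10,000 under the null):

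| Shape, placebo mean 4 / 5 / 6 | t-test power | Mann-Whitney power | Log-rank power | Three tests disagree | Any of three significant, no effect |
|---|---|---|---|---|---|
| Lognormal | 80.2 / 79.6 / 79.8 | 98.0 / 94.9 / 91.5 | 82.5 / 74.3 / 71.1 | 20.1 / 22.2 / 21.6 | 7.5 / 7.9 / 7.0 |
| Gamma | 80.6 / 80.7 / 80.5 | 93.8 / 89.5 / 86.8 | 72.7 / 69.3 / 68.1 | 21.7 / 21.2 / 19.7 | 7.7 / 7.4 / 7.4 |

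Weibull times are milder. Mann-Whitney power is 81-91%. At mean 6, normality is rejected in about 85% of trials, the three tests disagree in about 16-17%, and t-test and Mann-Whitney disagree in about 5%.

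Over all shapes and repeat runs at SD 2.5:
- Normality is rejected in about 85-100% of trials.
- Power is about 79-83% (t-test), 80-98% (Mann-Whitney) and 65-83% (log-rank).
- The three disagree in about 16-25% of trials; t-test and Mann-Whitney disagree in about 5-20%.

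At SD 2.0 the three disagree in about 9-14%, and normality is rejected in as few as about 40% of trials (Weibull, mean 6).

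**3. The two destinations for non-normal data.** With lognormal or gamma times at SD 2.5, a generalized model of the mean (AIC choosing among normal, gamma and inverse Gaussian) has 80-82% power against 87-98% for Mann-Whitney. They disagree in 8-16% of trials (2-5% at SD 2.0). If a lognormal model is among the candidates, disagreement falls to 1-4%.

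**4. Type I error.** A fixed rule ending in Mann-Whitney gives 4.7-5.5%. A fixed rule ending in the AIC-chosen model gives 5.0-6.6%. Taking the best of t-test, Mann-Whitney and log-rank gives about 6-8%.

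**5. Unresolved patients.** Completers still unresolved at Day 14 are about 1% of placebo or fewer under these assumptions, and dropping them leaves a difference of 0.98-1.02 day. For withdrawals the documents give no usable rate, because footnote 9's 10% is used up between 400 and 360. As a stress test only, suppose 5% of placebo and about 3% of Raphamin patients withdraw unresolved after Day 5. The true 1.0 day then becomes:

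| Handling | Estimated difference (days) |
|---|---|
| Dropped | 0.89-1.01 |
| Censored at withdrawal | 0.92-1.01 |
| Counted unresolved to Day 14 | 1.02-1.17 |
| Last diary day taken as the time | 0.88-0.96 |

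With no true effect and equal withdrawal in the arms, every rule tried stays near 5% error. Large inflation (about 25-29% when Day 14 is assigned) appeared only under an assumed 5% versus 15% imbalance.

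**The case against.** The strongest reply is that the hypothesis and formula already imply a two-sample comparison of means, and that Statistical criteria gives a conditional rule rather than a free choice. The mention of proportional risks and the listing of survival analysis show that censored-data methods were in view. The Per Protocol set behind the sizing excludes withdrawals. The document calls itself a protocol summary, so a fuller plan may settle these points.

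Much of this stands, and it limits the point. A reader might infer any of the following, which the documents do not support:

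- **That the plan inflates type I error to 7-8%.** That figure comes from picking the best of three tests. No section permits this, and a fixed rule stays near 5%.
- **That the selection rule leads only to methods needing a time for every patient.** Proportionality of risks is a Cox-model condition and survival procedures are listed; what is missing is the link to this endpoint.
- **That normality is certain to fail.** This depends on the assumed shape and SD.
- **That withdrawals bias the result.** The rates used above are assumptions, and the gap concerns only Full Analysis Set withdrawals and the few completers who never resolve.

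What the reply does not answer is that the rule moves the analysis off the sized t-test whenever normality fails, that two destinations then compete, and that no section gives a Full Analysis Set withdrawal a time or a censoring date.

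**Conclusion.** The gap is real and should be fixed; confidence is medium. It is a risk to the clarity and power of the primary comparison, not a demonstrated bias. The textual part (no assigned test, two unranked routes, no withdrawal rule) rests on the documents alone. Its size rests on assumed right-skewed times, placebo means of 4-6 days and a true difference of 1 day. On those assumptions the unstated choice of test alone decides significance in roughly one trial in six to one in four at SD 2.5, and in about 9-14% at SD 2.0. Log-rank contributes much of that, and a choice between t-test and Mann-Whitney alone matters less. The size of any withdrawal effect cannot be given without a withdrawal rate. The sample-size arithmetic is not in dispute.

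**What to change.** Before unblinding:

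1. Replace the data-driven choice for this endpoint with one named primary analysis that matches M1 - M2, and name its analysis set. The sizing is Per Protocol, so making the Full Analysis Set primary would be a deliberate change. Other tests become supportive. If log-rank is chosen instead, both the hypothesis and the size need rechecking.
2. Adjust for the Visit 1 total severity index. Its components are already collected: "At Visit 1 the parent/adoptive parent together with an investigator will record ARVI symptom severity and body temperature in the diary". By the plan's formula with SD multiplied by √(1 - R²), power at 100 per arm rises from 80.7% to 82.7%, 84.6% or 86.6% at an assumed R² of 5%, 10% or 15%.
3. State how withdrawals and unresolved patients are handled, for example censoring at the last diary entry. Because leaving for lack of efficacy may be informative, add a sensitivity analysis that counts such patients as unresolved to Day 14. It is a check, not a bound.
4. Reconcile how long diary symptoms are recorded, since the schedule marks the diary at Visit 4 but ARVI symptoms only to Visit 3, and the definition of resolution depends on later readings.

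One option for item 1 is the difference in restricted mean time to Day 14, which accepts censoring and keeps a result in days. Simulated with 5% random withdrawal at SD 2.5 (lognormal or gamma), its power is 79-83% unadjusted and 82-87% adjusted, with type I error 4.4-5.4%. It was not tested for error or power under informative withdrawal. It needs diary data to Day 14 and has less power than Mann-Whitney when times are skewed (79-86% unadjusted against 87-98%). Any single pre-specified analysis of M1 - M2 with a stated handling rule would close the gap.

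The cost is SAP wording and a little programming with procedures already listed (LIFETEST, GENMOD, PHREG). No extra patients are needed if a comparison of means is kept on the set used for the sizing.

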Per protocol set. This sample includes all patients who completed the therapy as per the study protocol and completed all the scheduled visits. This set will be used for the **Per Protocol analysis (PP analysis)** of the study therapy efficacy. *PP set* will not include the patients with their data completely or partially invalid for analysis due to a protocol deviation.

⁵ Holder of license: OOO “NPF “MATERIA MEDICA HOLDING”, No. 70100045.

The list of deviations that may result in complete or partial invalidity of data is developed by a medical expert jointly with a biostatistician according to the study design.

The deviations that may result in partial or complete invalidation of the study subject's data.

1. Inappropriate distribution/supply of the study drug.
2. Prescription of prohibited therapy.
3. Increase or decrease in the study drug dosing by $\geq 25\%$.
4. Inability to assess the patient's compliance using the formula (e.g. loss of pack with the product).
5. Major discrepancies between source documents and CRF identified during monitoring or another authorized inspection.
6. Violation of the procedure of obtaining informed consent.
7. Non-compliance with the clinical study protocol procedures.
8. Inability to collect all the patient's data used for evaluation of the study endpoints⁶ (e.g. lack of records in source documents required for verification of inclusion/exclusion criteria, safety and efficacy criteria).
9. Any other protocol deviations covered by the term “major deviation”.

Evaluation of sample size

It is expected that out of 360 patients randomized 200 patients will complete the study per protocol⁷. Taking into consideration the expected screening failures, the informed consent should be obtained from 400 patients.

The sample size was assessed on the basis of the following rules and assumptions:

1. Statistical provisions.
 - 1.1 the power of the statistical tests “ $P = (1 - \beta)$ ” is assumed to be 80% (the probability of correct rejection of the null hypothesis is 0.8);
 - 1.2 the probability of a type I error “ α ” is allowed to be less than 5% (the probability of false acceptance of an alternative hypothesis is less than 0.05);
 - 1.3 the applied statistical tests for group comparisons are two-sided, unless stated otherwise;
 - 1.4 the sample size is calculated based on the assumptions on the expected effect declared in the primary endpoint of this protocol;

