⁶ If, considering the lack of some data in primary endpoint variable, the fact of reaching the primary endpoint by the patient can still be determined, the patient will be eligible for PP analysis (e.g. the diary lacks some records but the time of recovery can still be determined).

⁷ No more than 10% patients who signed PIS and ICF are expected to be screening failures for various reasons.

1.5 the ratio between the sample sizes of the study drug and placebo groups is 1:1 (1 study drug patient - 1 placebo patient);

1.6 statistical hypotheses: null and alternative hypotheses about the superiority of the study drug over placebo using the applied dosing regimen:

primary endpoint:

$$H_0: M_1 - M_2 = 0$$

$$H_a: M_1 - M_2 \neq 0$$

where : M_1 – average time to resolution of the symptoms in the Raphamin group,

M_2 – average time to resolution of the symptoms in the Placebo group.

Sample analysis will be performed according to the following formulas:

$$n_1 = kn_2$$

$$n_2 = \frac{(z_{\alpha/2} + z_{\beta})^2 * (1 + 1/k)\sigma^2}{\varepsilon^2}$$

where n_2 , n_1 is sample size in study drug and placebo groups, respectively;

$\varepsilon = M_1 - M_2$ is the time difference between Raphamin and Placebo groups;

k – coefficient of Raphamin/Placebo sample ratio ($k=1$);

σ - standard deviation;

$z_{\alpha/2}$ – tabular value of two-sided z-test for α ;

z_{β} – tabular value of one-sided z-test for β ;

1.7 Full sample size is determined using the formula:

$$N = N_{pp} / (1 - R_w),$$

where N – the final sample size;

N_{pp} – result of calculation in cl. 1.6, i.e. scheduled number of the patients completing the study per protocol;

R_w – withdrawal rate.

2. Assumptions on expected effects of the clinical study: The differences in duration of the disease between the groups is expected to be less than 1 day, with standard deviation in the groups of no more than 2.5^8 days.

Therefore, the number needed to compare study drug and placebo will be **200** patients for both groups. Given potential withdrawal of at least 50%⁹ patients ($R_w = 0.5$) during the study for

⁸Upper limit of confidence interval of standard deviation of the time to resolution of the symptoms for placebo group based on the results of study MMH-ER-009 "International multicenter double-blind placebo-controlled randomized parallel-group clinical study of efficacy and safety of Ergoferon in the treatment of acute respiratory viral infections in children".

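### The primary comparison is framed and sized as an unadjusted difference in means, and no baseline covariate is pre-specified although three likely predictors are collected before dosing

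*Combined protocol and SAP*

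**What the plan says.** - **Hypothesis and sizing.** Evaluation of sample size, item 1.6, tests whether two means differ; the first is the "average time to resolution of the symptoms in the Raphamin group" and the second its placebo counterpart. The formula is the ordinary two-sample one with a marginal SD and no covariate term. Item 2 gives the assumed effect: "The differences in duration of the disease between the groups is expected to be less than 1 day". The SD assumed for each group is at most 2.5 days, and footnote 8 says that this figure is an upper confidence limit from an earlier paediatric study.
- **Error rates.** Items 1.1 to 1.3 set 80% power and a 5% type I error, and "the applied statistical tests for group comparisons are two-sided, unless stated otherwise".
- **Model.** Statistical criteria lists t-tests, general, generalized and mixed linear models, survival procedures and the Mann-Whitney test. None is assigned to the primary endpoint. ANCOVA appears only in a repeated-measures form for change over time, with no covariates named. Parametric criteria, item 5, adds that "specification of the factor and covariance structures of the model will be made using fit-statistics such as AIC".
- **Baseline data.** Study design states: "The nasopharyngeal swabs for PCR diagnosis and verification of respiratory viruses will be performed prior to therapy to confirm the viral etiology of ARVI". Axillary temperature and symptom scores are measured at the Visit 1 examination because they decide eligibility (inclusion criterion 2).
- **Covariates.** No section names a baseline variable as a covariate or stratification factor for the primary endpoint.

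**The concern.** Resolution is defined by temperature and by the number of remaining systemic symptoms, so the entry values of the same measures are natural candidates to predict how long resolution takes. The PCR-confirmed patients may also carry different viruses with different courses. A raw difference in means leaves any such variation in the error term. A fixed adjustment would remove some of it without more patients, visits or measurements.

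The plan neither commits to adjustment nor rules it out. The only rule it offers for choosing factors is a fit statistic computed on the trial's own outcome data. Precision that could be secured in advance is therefore left open, and so is the exact form of the primary treatment estimate.

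**Working it through.** **Inputs from the documents** (Evaluation of sample size): two-sided α = 0.05; power 0.80; difference ε = 1 day, the planning value behind the wording of item 2; σ = 2.5 days; ratio k = 1; 200 evaluable patients, 100 per group.

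**Assumed input:** R², the share of variance in time to resolution explained by the baseline covariates. The documents give no value, so 5%, 10% and 20% are shown.

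**1. Reproduce the plan's figure.**
n per group = 2(z_{α/2} + z_β)²σ²/ε² = 2 × (1.960 + 0.842)² × 2.5² / 1² = 98.1, rounded up to 99, or 198 in total. The plan states 200. Its size therefore follows from the unadjusted formula and takes no credit for covariates. The inflation also agrees: 200/(1 − 0.5) = 400.

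**2. Power with adjustment.** In a linear model the residual SD is 2.5 × √(1 − R²). Power is from the two-sample t-test with 100 per group and noncentrality 1/(residual SD × √(2/100)). The few degrees of freedom used by the covariates are ignored. The equivalent unadjusted sample size is 200/(1 − R²).

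| R² | Residual SD (days) | Noncentrality | Power at 1 day | Equivalent unadjusted N |
|---|---|---|---|---|
| 0 | 2.500 | 2.828 | 80.4% | 200 |
| 5% | 2.437 | 2.902 | 82.3% | 211 |
| 10% | 2.372 | 2.981 | 84.3% | 222 |
| 20% | 2.236 | 3.162 | 88.2% | 250 |

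**3. Sensitivity to the difference.** Item 2 expects less than 1 day. At 0.8 day (illustrative), the same calculation gives 61.5% unadjusted, 66.0% at R² = 10% and 71.1% at R² = 20%.

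**4. Sensitivity to the SD.** The planning SD is an upper limit. At SD 2.2 days (illustrative), unadjusted power for 1 day is already about 89%.

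**The case against.** An unadjusted comparison of randomized groups is valid, and adjustment is not needed to reach the planned power. That stands: this is a point about efficiency.

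The gain is also unproven. No R² is given. Entry requires at least 37.8 °C, minimum symptom scores and the first 24 hours of illness, which narrows the range of two of the three covariates. At R² = 5% the gain is only 1.9 percentage points. The virus panel and expected mix are not described, so some categories may be sparse. All of this stands; it is why the result is shown as a range and why the fix pools sparse categories.

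Item 5 is a generic line and is not tied to the primary endpoint. That is also correct, but Statistical criteria covers all calculations and no primary model overrides it.

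Four stronger readings are tempting, and the documents do not support them:

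- **The baseline data will be ignored.** ANCOVA, the linear-model procedures or PHREG could bring them in. They are not pre-specified, which is a different statement.
- **AIC selection inflates the type I error.** In null simulations with AIC choosing among main effects only, rejection rates were 4.9% against 4.8% unadjusted, 4.5% against 4.3%, and 6.5% against 6.0% in three separate runs: gaps of 0.1 to 0.5 percentage points. Marked inflation needs treatment-by-factor interactions and an effect read at one reference level. The plan describes neither.
- **AIC is unusable because REML fits with different fixed factors cannot be compared.** That concerns PROC MIXED under its default fit, and nothing sends the primary endpoint through that procedure.
- **Power is only just 80%.** The SD is an upper confidence limit, so power for a 1-day difference may be higher. The wording about less than 1 day pulls the other way, but that is a separate sizing question.

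**Conclusion.** The point holds as a matter of precision and pre-specification. The primary comparison is framed and sized without covariates, no covariate is fixed, and the only stated rule for choosing factors is a fit statistic. At 1 day and SD 2.5, adjustment would raise power from 80.4% to between 82.3% and 88.2% for an assumed R² of 5% to 20%, equivalent to 11 to 50 extra evaluable patients (211 − 200 and 250 − 200).

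This rests on the assumed R² and on a linear analysis of mean time to resolution, which is the hypothesis that the plan states. The √(1 − R²) arithmetic does not carry over to a Cox or log-rank analysis. The planned 200 evaluable and 400 consented patients do not need to change.

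**What to change.** For the primary endpoint, replace the selection of factors by AIC with one named model, fixed before unblinding:

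- A linear model (ANCOVA) of time to resolution, or another named model that matches the stated mean-difference hypothesis.
- Treatment plus fixed main effects for temperature at the Visit 1 examination, symptom score at the same examination, and virus group from the pre-therapy swab.
- A virus grouping defined before unblinding, with a rule for pooling sparse categories.
- No treatment-by-covariate interactions in the primary model.
- The unadjusted comparison reported as a sensitivity analysis.

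If a survival model is chosen instead, include the same covariates and state that the adjusted hazard ratio is a different estimand from the difference in means in item 1.6. The hypothesis should then be restated to match.

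The cost is SAP wording. All three variables are already scheduled for collection, and no extra patients, visits or tests are needed.
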